9.2.2 Sample Size Calculation for the Immunogenicity Endpoints

The primary objective of this study is to evaluate the magnitude and durability of SARS-CoV-2 specific antibody titers in serum samples. This objective is descriptive in nature and will be accomplished by estimating 95% confidence intervals (CI) for the geometric mean titer (GMT) at each timepoint when samples are collected.

The precision with which the GMT can be estimated from observed data depends on the standard deviation (SD) of the measurements, on the logarithmic scale, and the sample size. [Table 6](#) displays two-sided 95% confidence intervals for the GMT for several values of the observed antibody titer. [Table 6](#) also shows results assuming up to 10% attrition.

Table 6: Two-sided 95% confidence intervals based on observing a particular average \log_e -antibody titer in subjects' vaccine groups and potential strata sizes

Observed average \log_e antibody titer	SD of \log_e antibody titer	95% confidence interval of GMT in vaccine groups and strata			
		N = 100	N = 50	N = 25	N = 15
$\log_e(5)$	0.5	(4.5, 5.5)	(4.3, 5.8)	(4.1, 6.1)	(3.8, 6.6)
$\log_e(20)$		(18.1, 22.1)	(17.4, 23.1)	(16.3, 24.6)	(15.2, 26.4)
$\log_e(50)$		(45.3, 55.2)	(43.4, 57.6)	(40.7, 61.5)	(37.9, 66)
$\log_e(100)$		(90.6, 110.4)	(86.8, 115.3)	(81.4, 122.9)	(75.8, 131.9)
$\log_e(250)$		(226.4, 276.1)	(216.9, 288.2)	(203.4, 307.3)	(189.5, 329.8)
$\log_e(500)$		(452.8, 552.1)	(433.8, 576.3)	(406.8, 614.6)	(379.1, 659.5)
$\log_e(1000)$		(905.6, 1104.3)	(867.5, 1152.7)	(813.5, 1229.2)	(758.1, 1319)
$\log_e(5)$	1.0	(4.1, 6.1)	(3.8, 6.6)	(3.3, 7.6)	(2.9, 8.7)

Observed average \log_e antibody titer	SD of \log_e antibody titer	95% confidence interval of GMT in vaccine groups and strata			
		N = 100	N = 50	N = 25	N = 15
\log_e (20)		(16.4, 24.4)	(15.1, 26.6)	(13.2, 30.2)	(11.5, 34.8)
\log_e (50)		(41, 61)	(37.6, 66.4)	(33.1, 75.6)	(28.7, 87)
\log_e (100)		(82, 121.9)	(75.3, 132.9)	(66.2, 151.1)	(57.5, 174)
\log_e (250)		(205, 304.9)	(188.2, 332.2)	(165.5, 377.8)	(143.7, 435)
\log_e (500)		(410, 609.7)	(376.3, 664.3)	(330.9, 755.5)	(287.4, 869.9)
\log_e (1000)		(820, 1219.5)	(752.6, 1328.7)	(661.8, 1511)	(574.8, 1739.8)

* Assumes approximately 10% attrition.

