9.2 Sample Size Determination

9.2.1 Sample Size Calculation for the Safety Endpoint

Rare AEs are not demonstrable in a clinical study of this size; however, the probabilities of observing one or more AEs given various true event rates are presented in [Table 5](#). With the assumption that all enrolled subjects will likely complete immunizations and safety visits in this relatively short duration study, the following statistical considerations apply. With approximately 100 subjects in each arm there is a greater than 99.9% chance of observing at least one AE of probability 10%. With approximately 50 subjects in each of the strata subgroups (or arms), there is a 99.5% chance of observing at least one AE of probability 10%. With approximately 25 subjects in each of the strata subgroup combinations (assuming equal numbers and 100 per arm), there is a 92.8% chance of observing at least one AE of probability 10%. Finally, with approximately 15 subjects in the smallest of the strata subgroup combinations (assuming unequal numbers and 100 per arm or 50 per arm), there is a 79.4% chance of observing at least one AE of probability 10%. Therefore, if no AEs of a given type occur in a group (or strata), we can be relatively confident that they will occur in fewer than 10% of people if the vaccine is implemented.

Table 5: Probability of Observing one or more Adverse Event for Various Event Rates in one vaccine group (or strata).

N	“True” Event Rate	Probability of Observing \geq 1 events (%)	N	“True” Event Rate	Probability of Observing \geq 1 events (%)
100	0.1%	9.5	50	0.1%	4.9
	0.5%	39.4		0.5%	22.2
	1.0%	63.4		1.0%	39.5
	2.0%	86.7		2.0%	63.6
	3.0%	95.2		3.0%	78.2
	4.0%	98.3		4.0%	87
	5.0%	99.4		5.0%	92.3
	10.0%	>99.9		10.0%	99.5
	15.0%	>99.9		15.0%	>99.9
	20.0%	>99.9		20.0%	>99.9
	30.0%	>99.9		30.0%	>99.9

N	“True” Event Rate	Probability of Observing ≥ 1 events (%)	N	“True” Event Rate	Probability of Observing ≥ 1 events (%)
25	0.1%	2.5	15	0.1%	1.5
	0.5%	11.8		0.5%	7.2
	1.0%	22.2		1.0%	14
	2.0%	39.7		2.0%	26.1
	3.0%	53.3		3.0%	36.7
	4.0%	64.0		4.0%	45.8
	5.0%	72.3		5.0%	53.7
	10.0%	92.8		10.0%	79.4
	15.0%	98.3		15.0%	91.3
	20.0%	99.6		20.0%	96.5
	30.0%	>99.9		30.0%	99.5

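### Table 6 claims to allow for about 10% attrition, but every interval in it is computed at the full N

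*Protocol*

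**What the plan says.** Section 9.2.2 treats the primary objective as estimation of GMTs with 95% confidence intervals at each sampling time, and says the precision "depends on the standard deviation (SD) of the measurements, on the logarithmic scale, and the sample size". Table 6 then "displays two-sided 95% confidence intervals for the GMT for several values of the observed antibody titer", for two SDs of the log titer (0.5 and 1.0) and four sizes (100, 50, 25, 15).

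Attrition is mentioned twice in that section. The text says the table "also shows results assuming up to 10% attrition", and the footnote below the table says "Assumes approximately 10% attrition". There are no separate columns for reduced sizes.

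The four sizes are explained in section 9.2.1, where they serve the safety calculation under the assumption that all enrolled subjects complete vaccination and safety visits:

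- 100: "With approximately 100 subjects in each arm there is a greater than 99.9% chance of observing at least one AE"
- 50: "With approximately 50 subjects in each of the strata subgroups (or arms"
- 25: "With approximately 25 subjects in each of the strata subgroup combinations (assuming equal numbers and 100 per arm"
- 15: "with approximately 15 subjects in the smallest of the strata subgroup combinations"

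Table 1 plans 100 subjects per arm in stages 1 and 4 and 50 per arm in stages 2 and 3. Section 7.2 states that vaccinated subjects who withdraw or are lost are not replaced.

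**The concern.** The same four sizes appear in Table 5, where nobody is lost, and in Table 6, where a tenth are said to be lost. If 100 and 50 are enrolled arm sizes, an interval allowing for 10% loss has to be computed on 90 and 45.

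The trial tests no hypothesis (section 9.1), so interval width is the whole quantitative rationale for the size of the primary immunogenicity evaluation, and Table 6 is the only place it is given. A reader who trusts the footnote will make no further allowance for dropout. The allowance would probably matter most at the late visits (Day 366 in the single-dose schedule, Day 422 in the two-dose schedule). That is an inference, because the protocol gives no attrition by visit.

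**Working it through.** **Inputs.** From section 9.2.2: two-sided 95% confidence, SD of the log titer 0.5 or 1.0, and attrition of about 10%. From Table 6: N = 100, 50, 25, 15 and seven GMT values. From Table 1: 100 or 50 enrolled per arm.

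**Formula.** Interval = GMT × exp(± h), with h = t(0.975, n − 1) × SD / √n.

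**Step 1: reproduce the printed table.** For GMT 1000, SD 0.5 and n = 100: h = 1.984 × 0.5 / 10 = 0.0992, so the interval is 1000 × exp(± 0.0992) = (905.6, 1104.3), exactly as printed. The table holds 7 × 2 × 4 = 56 intervals. All 56 agree to printed rounding at n = 100, 50, 25 and 15.

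**Step 2: apply the stated loss.** 0.9 × 100 = 90; 0.9 × 50 = 45; 0.9 × 25 = 22.5, taken as 22 or 23; 0.9 × 15 = 13.5, taken as 13 or 14. Results for GMT 1000:

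| N | SD | Printed | With about 10% loss |
|---|---|---|---|
| 100 | 0.5 | (905.6, 1104.3) | n = 90: (900.6, 1110.4) |
| 50 | 0.5 | (867.5, 1152.7) | n = 45: (860.5, 1162.1) |
| 25 | 0.5 | (813.5, 1229.2) | n = 23: (805.6, 1241.4); n = 22: (801.2, 1248.2) |
| 15 | 0.5 | (758.1, 1319) | n = 14: (749.2, 1334.7); n = 13: (739.2, 1352.8) |
| 100 | 1.0 | (820, 1219.5) | n = 90: (811.0, 1233.0) |
| 50 | 1.0 | (752.6, 1328.7) | n = 45: (740.5, 1350.4) |
| 25 | 1.0 | (661.8, 1511) | n = 23: (648.9, 1541.0); n = 22: (641.9, 1558.0) |
| 15 | 1.0 | (574.8, 1739.8) | n = 14: (561.4, 1781.4); n = 13: (546.5, 1830.0) |

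Over all 56 entries, one matches at the reduced size: GMT 5, SD 0.5, N = 50. There n = 45 gives 5 × 0.8605 = 4.3 and 5 × 1.1621 = 5.8, so one-decimal rounding hides the difference. No whole column matches.

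**Step 3: rule out a different method at a smaller n.** A search over n = 5 to 129 for the GMT 1000 rows finds only n = N with the t quantile. With the normal quantile no n reproduces the printed limits; the nearest are 98, 48, 23 and 13.

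**Step 4: size of the understatement.** Half-widths h at SD 1.0, with increases taken from unrounded values (the percentages are the same at SD 0.5):

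| N | h as printed | h with loss | Increase |
|---|---|---|---|
| 100 | 0.1984 | 0.2094 (90) | 5.6% |
| 50 | 0.2842 | 0.3004 (45) | 5.7% |
| 25 | 0.4128 | 0.4324 (23) to 0.4434 (22) | 4.8% to 7.4% |
| 15 | 0.5538 | 0.5774 (14) to 0.6043 (13) | 4.3% to 9.1% |

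**Step 5: could N already be net of attrition?** That would need 100 / 0.9 = 111.1, 50 / 0.9 = 55.6, 25 / 0.9 = 27.8 and 15 / 0.9 = 16.7, so 112, 56, 28 and 17 enrolled. Table 1 gives arms of 100 and 50.

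**The case against.** The best defence is that N is the number observed, not the number enrolled. The title of Table 6 speaks of an observed average in groups and potential strata, which allows that reading. In stages 1 to 3 the 18 to 64 age group is about 55% of an arm; after 10% loss that is 0.9 × 55 = 49.5 of a 100-subject arm, or 0.9 × 27.5 = 24.75 of a 50-subject arm, close to the 50 and 25 columns. The arms in Table 1 also sum to 6 × 100 + 6 × 50 + 3 × 50 + 2 × 100 = 1,250, against planned enrolment of about 1,500, so some headroom may exist.

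This does not rescue the table. The stratum reading cannot explain N = 100, or N = 50 as a whole arm in stages 2 and 3. Section 9.2.1 builds the 25 from an equal split of a full 100-subject arm. The extra 250 subjects are nowhere assigned to dropout, and section 4.1 foresees added arms or larger samples.

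The asterisk has no visible anchor in the text as read, so it may have marked only some entries. That changes nothing, since no printed column fits a 10% loss.

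The argument about consequence largely stands. For a whole arm at SD 0.5 each limit moves by only about 0.55% (5.0 / 905.6 and 6.1 / 1104.3). Going from SD 0.5 to SD 1.0 doubles the half-width on the log scale, so uncertainty about the SD matters far more. The text says up to 10%, which makes 5.6% and 5.7% upper bounds for whole arms. The 9.1% figure needs 2 of 15 lost, slightly more than 10%.

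**Conclusion.** The concern holds. The sentence and the footnote in section 9.2.2 are wrong for every column of Table 6: the intervals assume complete data at 100, 50, 25 and 15. Under the protocol's own 10% assumption, the log-scale half-width is understated by 5.6% for a 100-subject arm and 5.7% for a 50-subject arm. For the smaller groups the understatement is 4.8% to 7.4% (N = 25) and 4.3% to 9.1% (N = 15), depending on how fractional subjects are rounded. These figures rest on t-based intervals, which the printed values confirm, and on the protocol's assumed SDs and attrition.

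The arm sizes are not invalidated: there is no precision target, power statement or margin that the corrected intervals would miss, and reported intervals will use the actual n and SD. It should still be corrected, because it is a false statement in the only quantitative precision argument for the primary endpoint.

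**What to change.** Either of two changes resolves it:

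1. Recompute Table 6 at 90, 45, 22 to 23 and 13 to 14, stating the rounding rule, or add those columns beside the existing ones. Adding columns would also fit the text, which presents the attrition results as an addition.
2. Keep the figures, delete the attrition sentence and the footnote, and state that the intervals assume complete data at the N shown.

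If N was meant as evaluable subjects, the protocol should say so and give the matching enrolment per arm (112 and 56 for the whole-arm columns), which Table 1 does not. The cost of either change is a table or text correction. The first gives slightly wider intervals; neither alters the design, the analysis or the care of participants.

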9.3 Populations for Analyses

The safety analysis population includes all enrolled subjects who received at least one dose of study vaccine. Analyses for the safety population will include safety reported through the end of the study. The modified intent-to-treat (mITT) population includes all subjects who received at least one dose of vaccine and contributed both pre- and at least one post-vaccination venous blood sample for immunogenicity testing for which valid results were reported.

In the final analysis, protocol deviations will be reviewed to determine which protocol deviations may affect the analysis. The per protocol (PP) population will then be defined – and this includes all subjects in the mITT subset with the following exclusions:

- Data from all available visits for subjects found to be ineligible at baseline.
- Data from all visits subsequent to the protocol deviations that are considered to affect the science.
- Data from any visit that occurs substantially out of window.

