4.2 Scientific Rationale for Study Design

An open-label study will facilitate the need for rapid review and dissemination of study data for public health reasons. Safety findings are not expected to be dissimilar from Phase 1/2/3 studies conducted for similar vaccine constructs. Randomization will improve comparisons between the different arms. Each stage will contain an arm with the prototype vaccine with the exception of stage 4.

Selected arms will assess 2 study doses of vaccine candidates to assess if 2 doses provide a more durable response and more specific to variant viruses.

We chose the interval of 4 months since a recent study performed by our investigators showed that an interval of 3 months between primary series and boost had acceptable safety and immunogenicity responses.¹⁹

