9. STATISTICAL CONSIDERATIONS

9.1 Statistical Hypotheses

This is a phase 2, open-label, multi-site clinical trial that is not designed to test a specific hypothesis. Rather, it is intended to obtain preliminary estimates in adults of the safety and immunogenicity of additional booster doses of SARS-CoV-2 variant vaccines.

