9.4.2 Analysis of the Primary Endpoint(s)

Descriptive summaries of immunogenicity data will be presented for the mITT population. If there are protocol deviations which may affect the analysis, a per-protocol (PP) analysis may also be performed.

Geometric Mean Titers (GMT) and Geometric Mean Fold Rise (GMFR) from baseline of SARS-CoV-2 specific antibody binding and neutralization titers will be calculated, along with 95% CIs, for all groups, at each timepoint. Summaries will also be displayed graphically. Geometric Mean Ratio (GMR_{D614G}) is defined as the ratio of a variant of concern to D614G (i.e Beta to D614G) will also be reported for all groups, at each timepoint, along with 95% CIs.

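### GMT and GMFR are fixed on mITT at every visit with no cut for titres drawn after breakthrough infection or an outside COVID-19 vaccine, so late summaries can understate waning

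*Protocol*

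**What the plan says.** Protocol 9.2.2 states: "The primary objective of this study is to evaluate the magnitude and durability of SARS-CoV-2 specific antibody titers in serum samples". Section 4.2 explains that selected arms receive two doses "to assess if 2 doses provide a more durable response". The formal objective in section 3 is broader: it names humoral responses only, with an endpoint covering all timepoints.

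Section 9.4.2 sets the population: "Descriptive summaries of immunogenicity data will be presented for the mITT population". GMT and GMFR "will be calculated, along with 95% CIs, for all groups, at each timepoint". Tables 2 and 3 carry serum collection to D366 (one dose) and D422 (two doses). Under 9.3 the mITT set "includes all subjects who received at least one dose of vaccine and contributed both pre- and at least one post-vaccination venous blood sample", provided valid results were reported. That definition selects subjects, not visits.

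The only cut triggered by an event is in the per-protocol set, which drops "Data from all visits subsequent to the protocol deviations that are considered to affect the science". If deviations may affect the analysis, "a per-protocol (PP) analysis may also be performed". Section 10.1.9.4 defines a deviation as non-compliance. Section 8.1.5 records confirmed infection as an exploratory efficacy assessment. Section 6.5 requires COVID-19 vaccines received outside the study to be captured, and footnote m to Tables 2 and 3 arranges a visit around a planned outside booster.

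**The concern.** A titre drawn after an infection or an outside booster reflects that exposure as well as the study vaccine. Under the stated rules it enters the late-visit GMT and GMFR on the same footing as any other. Where the exposure leaves titres higher than they would have been, the shift is upward and the decline looks smaller than the study vaccine alone would give.

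The per-protocol set does not reliably correct this. Becoming infected is not non-compliance. An outside booster in Stages 1–3 is not clearly non-compliance either, since footnote m accommodates it.

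At stake is the reading of the late visits, including whether two doses last longer than one.

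**Working it through.** **Visits open to a planned outside vaccine.** Exclusion 7 bars planned vaccines within 28 days of a dose. Exclusion 17 (Stage 4 only) bars a planned outside booster for 180 days.

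- Single dose, Stages 1–3: day 1 + 28 = D29. Of D15, D29, D91, D181, D271 and D366, four of six lie beyond the bar.
- Stage 4: day 1 + 180 = D181. D271 and D366 lie beyond it, two of six.
- Arm 3 after dose 2: D57 + 28 = D85. Of D71, D85, D147, D237, D327 and D422, four of six lie beyond it.

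These counts show when outside boosting is not barred, not how often it happens. D15 and D29 should be little affected by planned vaccines. Infection can precede any visit. Subjects infected or vaccinated outside the study before dose 2 do not receive it and revert to the single-dose schedule (1.2, 7.1.4), so that route does not affect the post-dose-2 visits.

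**Reproducing Table 6.** The upper CI factor is exp(t(0.975, n−1) × SD/√n), with n the full column size. At SD 1.0 it is 1.2195 (n=100) and 1.3287 (n=50). At SD 0.5 it is 1.1043 and 1.1527. For a GMT of 1000 these give upper limits of 1219.5, 1328.7, 1104.3 and 1152.7, as printed.

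**Shift in the late GMT.** Let p be the share of titres at a visit drawn after a new exposure, and f the fold excess still present. The mean log titre rises by p × ln f, so GMT is multiplied by f^p. So is GMFR, because the baseline is untouched. The protocol gives neither p nor f; both are assumed here. The value f=9 is an upper case: the 9 to 10 fold in section 4.3 is a rise after a dose, not an excess remaining later.

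| p | f | f^p | An assumed true 4.0-fold decline would appear as |
|---|---|---|---|
| 5% | 2 | 1.035 | 4/1.035 = 3.86 |
| 10% | 2 | 1.072 | 4/1.072 = 3.73 |
| 10% | 3 | 1.116 | 4/1.116 = 3.58 |
| 20% | 3 | 1.246 | 4/1.246 = 3.21 |
| 20% | 9 | 1.552 | 4/1.552 = 2.58 |

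**Share at which the shift equals the upper CI factor**, p = ln(CI factor)/ln f:

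| n, SD | f=2 | f=3 | f=9 |
|---|---|---|---|
| 100, 1.0 | 28.6% | 18.1% | 9.0% |
| 50, 1.0 | 41.0% | 25.9% | 12.9% |
| 100, 0.5 | 14.3% | 9.0% | 4.5% |
| 50, 0.5 | 20.5% | 12.9% | 6.5% |

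**Price of a cut.** At SD 1.0 the CI factor moves from 1.220 to 1.226 (n=95) or 1.249 (n=80), and for an arm of 50 from 1.329 to 1.377 (n=40).

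The cut can also bias. If exposed subjects would otherwise have had log titres lower by d, the cut summary is raised by exp(p × d). For an assumed d=0.5 that is exp(0.025) = 1.025 at p=5% and exp(0.10) = 1.105 at p=20%. The cut summary is the more biased of the two when d exceeds ln f, which is 0.69 for f=2 and 1.10 for f=3.

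**The case against.** The strongest reply is that this belongs in the SAP. Section 9.4 promises a full SAP before the primary data lock, and a visit-level censoring rule is ordinary SAP content. The trial is "not designed to test a specific hypothesis", so an all-data descriptive summary is legitimate. Section 9.2.2 also goes on to say that the objective will be met by estimating the GMT with its CI at each timepoint, which is what 9.4.2 delivers. Footnote m may let the visit arranged around a planned booster stand in for the next scheduled one. The review team could class an outside vaccine as a deviation. Finally, the size is assumed throughout, and the cut brings its own bias.

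Much of this stands. The all-data summary should stay, the size is unknown, and the SAP, not seen here, may already hold a rule. But the point concerns what the protocol fixes, not a detail it leaves open. Followed exactly, its rules count post-exposure titres towards durability, and its one event-based cut is keyed to a trigger that misses infection. The substitute visit protects only the next scheduled sample. The per-protocol set, which drops visits substantially out of window without giving a threshold, could discard that sample and keep later ones. Sections 9.4 and 9.4.6 also allow abbreviated analysis plans and publication while the study is running, so results may appear before the full SAP.

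**Conclusion.** The concern holds as a cheap improvement, with medium confidence. The protocol's only fixed immunogenicity summary does not isolate the durability of the study-vaccine response, and it can understate waning at late visits. For any f above 1 the shift is upward. Its size depends on p and f, which the protocol does not supply: ×1.04 to ×1.25 over the moderate assumptions and ×1.55 in the upper case. Against Table 6 at SD 1.0 and n=100, a 2-fold residual excess needs about 29% of titres affected before the shift matches the CI factor; a 3-fold excess needs about 18%. The effect may be negligible or material.

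**What to change.** In 9.3 and 9.4.2, keep the all-data mITT summary and add a named durability summary of GMT and GMFR for all arms. It excludes a subject's results after the earlier of:

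- the first confirmed SARS-CoV-2 infection as defined in 8.1.5;
- the first COVID-19 vaccine or SARS-CoV-2 antibody product received outside the study, as recorded under 6.5.

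Use anti-nucleocapsid conversion as a further trigger only where the assay is run and the baseline was negative. Report the number excluded per arm and visit. Interpret the two summaries together, because the exclusion may be informative and can itself raise the late GMT.

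The cost is analysis wording; no new data are needed. A protocol edit requires IRB approval (10.1), so it could go into the next amendment. The precision loss is small and the possible censoring bias is as calculated above. Some infections will still be missed: untested asymptomatic cases stay in, and with about 40% expected to have prior infection (4.1), anti-nucleocapsid conversion could inform at most roughly 100% − 40% = 60% of subjects.

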9.4 Statistical Analyses

Interim analyses of safety and immunologic response data will be done, as needed.

The final analysis will be performed after the final data lock and clinical study report (CSR) completed when all primary safety endpoint data and all secondary immunogenicity endpoint data are available and received by the SDCC. Any available data from the exploratory immunogenicity endpoints may also be included in the CSR. Remaining exploratory immunogenicity endpoint data may be included in an addendum to the CSR, publication of manuscript(s), or other report(s). Abbreviated analysis plans that describe planned analyses to facilitate dissemination of study data for public health reasons, including manuscript publication(s), will be developed by the SDCC as needed. A full statistical analysis plan (SAP) will be developed by the SDCC and finalized prior to the primary data lock.

